# Clinical Study Protocol

## Johnson & Johnson Vision Care, Inc.

### 14.5. Primary Analyses

#### **Phase I (interim analysis):**

For photopic and mesopic contrast sensitivity, the logarithm of contrast sensitivity will be calculated as  $logCS = log_{10}(1/(contrast\ threshold/100))$  and the logCS will be used for the analysis purpose. Note that *contrast threshold* is reported in percentage (%) in the Electronic Data Capture system. Photopic and mesopic logCS will be analyzed separately using linear mixed effects models with a normal distribution. The dependent variable will be the logCS and light source condition (i.e., without glare and with glare) will be the fixed effect in both models. A subject-specific random intercept will be included to account for repeated measurement on the same individuals. The least-square means (LSM, i.e., adjusted means) of photopic and mesopic logCS at 6 cpd will be estimated with 95% confidence interval under each light source condition. The reduction in the estimated means due to the glare source will be compared against the criteria of 0.1 log. If the reduction in the estimated mean due to the glare source is about 0.1 log units, it can be concluded that the glare light source is verified and the study can move to Phase 2.

#### **Phase 2:**

Superiority testing with respect to the primary endpoint in phase 2 will be assessed on the Intent-to-Treat (ITT) population.

#### Photopic Resolution Acuity using Landolt C's with a Glare Source

The photopic resolution acuity using Landolt C's (converted to logMAR unit using  $logMAR = log_{10}(arcminute)$ ) will be analyzed under bright light conditions with a broadband light source (glare) using a linear mixed model with a normal distribution. Lens type, dominant eye, and the interaction of lens type by dominant eye will be included in the model as fixed effects and age as a covariate. The covariance of residuals between eyes within the same subject (R-side) will be modeled using Unstructured (UN) covariance structure. If the model does not converge, then a compound Symmetry (CS) covariance structure will be considered. The Kenward and Roger method (Kenward and Roger, 1997) will be used for the denominator degrees of freedom.

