# **Clinical Study Protocol**

## **Johnson & Johnson Vision Care, Inc.**

### **5. TEST ARTICLE ALLOCATION AND MASKING**

#### **5.1. Test Article Allocation**

Phase 1: Not Applicable. Subjects are wearing their habitual contact lenses.

Phase 2: Use of the test articles will be randomized using a lens fitting schedule supplied by the study biostatistician. The clinical site will follow the lens fitting schedule provided and will complete enrollment according to the randomization list and will not pre-select or pre-assign subjects.

Randomly-permuted block randomization will be used to avoid bias in the assignment of subjects to treatment and to enhance the validity of statistical comparisons across treatment groups. Subjects, in blocks of two, will be randomized to either wear the Test lens in the left eye and the Control lens in the right eye or the Control lens in the left eye and the Test lens in the right eye. The order of the light sources is predetermined: visual performance will be assessed under the no broadband light source (without glare) condition first and then assessed under the broadband light source (with glare) condition. The same randomization scheme will be used for these two light sources. Under each light source condition, the right eye will always be tested first. Subjects will be stratified into one of two age groups (18-39 years old and 40-70 years old) using a 1:1 allocation ratio. The randomization scheme will be generated using the PROC PLAN procedure from Statistical Analysis System (SAS) Software Version 9.4 or higher (SAS Institute, Cary, NC).

Randomization will be performed at phase 2 visit 1. The following must have occurred prior to randomization:

- Informed consent must have been obtained.
- The subject must have met all eligibility criteria.
- The subject's screening and baseline information must have been collected.

When releasing test articles for vision testing, the following steps should be followed to maintain randomization codes:

1. Investigator or designee (documented on the Delegation Log) will consult the lens fitting schedule to obtain the test article assignment for that subject prior to dispensing.
2. Investigator or designee will record the subject's number on the appropriate line of the lens fitting schedule.

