**Clinical Study Protocol**  
**Johnson & Johnson Vision Care, Inc.**

Phase 2: Visit 1: Baseline		
Step	Procedure	Details
1.18	Entrance Visual Acuity	Record the distance Snellen visual acuity (OD, OS, and OU) to the nearest letter with their habitual spectacle. Subjects must read the smallest line until at least 50% of the letters are read incorrectly.
1.19	Subjective Sphero-cylindrical Refraction	Complete subjective sphero-cylindrical refraction and record the resultant distance visual acuity (OD, OS, and OU) to the nearest letter.
1.20	Eye Dominancy	The investigator will determine eye dominancy of the subject by first using the +1.00 blur test. If this fails to determine dominancy, then the sighting test will be used.
1.21	Slit Lamp Biomicroscopy	
FDA Slit Lamp Classification Scale will be used to grade the findings.
 
If any of these slit lamp findings are grade 3 or higher, the subject may not continue at this time, but may return up to one additional time to determine eligibility. If discontinued a final examination must be completed.
 
If the clearance of the fluorescein needs to be expedited, preservative-free rewetting drops or saline may be instilled.

1.22	Eligibility after Baseline	
All responses to Inclusion Criteria questions must be answered “yes” and all responses to Exclusion Criteria questions must be answered “no” for the subject to be considered eligible.
 
If subject is deemed to be ineligible after baseline, proceed to Final Evaluation and complete Subject Disposition. Refraction and Biomicroscopy forms do not need to be completed as part of Final Evaluation.

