**Clinical Study Protocol**  
**Johnson & Johnson Vision Care, Inc.**

Phase 2: Visit 1: Treatment 1 Lens Fitting		
Step	Procedure	Details
		
mean +/- SD for each spatial frequency. Range 0.0000 – 100.0000.
 
F. Rest a minimum of 2 minutes before next test
 
With glare OS:            Steps 1-3 listed above will be repeated for the alternate eye.

1.35	Lens Removal	The worn study lenses will be removed and discarded.

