#### Mesopic Contrast Sensitivity with a Glare Source

The AULCSF for mesopic contrast sensitivity testing under dim light conditions with a broadband light source (glare) will be analyzed, tested, and interpreted in the same manner as the analysis of the AULCSF for photopic contrast sensitivity.

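### The three Phase 2 models omit an OD/OS (test-order) term although lens is randomised to eye and OD is always tested first, so any OD–OS shift inflates the standard error of the lens difference

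*Combined protocol and SAP*

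**What the plan says.** **Allocation and order (Section 5.1).** Allocation is by eye: "Subjects, in blocks of two, will be randomized to either wear the Test lens in the left eye" with Control in the right, or the reverse, stratified by two age groups. The order of testing is fixed: "Under each light source condition, the right eye will always be tested first".

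**Procedure (Section 7.2, steps 1.33 and 1.34).** The right eye completes resolution acuity, photopic contrast and mesopic contrast, and then "Steps 1-3 listed above will be repeated for the alternate eye". This is done first without glare and then with glare. The untested eye is patched, and minimum rests of 2 or 5 minutes separate the tests.

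**Models (Sections 14.5 and 14.6).** For the primary endpoint, "Lens type, dominant eye, and the interaction of lens type by dominant eye will be included in the model as fixed effects", with age as covariate. For the two eyes of a subject, "The covariance of residuals between eyes within the same subject (R-side) will be modeled using Unstructured (UN) covariance structure", with compound symmetry as fallback. The photopic AULCSF model has the same terms, and the mesopic AULCSF "will be analyzed, tested, and interpreted in the same manner as the analysis of the AULCSF for photopic contrast sensitivity". None of the three has a term for right versus left eye or for test order.

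**Dominance (Section 7.2, step 1.20).** "The investigator will determine eye dominancy of the subject by first using the +1.00 blur test", with a sighting test as backup. It is a property found for each subject and is not the same variable as OD/OS.

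**The concern.** Every subject contributes one Test eye and one Control eye, and the right eye always goes first. If right and left eyes differ on average, or if fatigue, practice or adaptation moves results between the first and second eye, that shift enters each subject's Test minus Control difference. Its sign depends only on which eye was randomised to Test.

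With balanced allocation the shift averages out of the lens estimate. Without an eye term it does not leave the residual: half the differences are pushed up and half down, and the model reads this as noise.

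The planned terms do not deal with it. The unstructured covariance describes how the two eyes vary together and does not represent a mean difference between them. The dominant-eye term, if coded per eye, stands in for OD/OS only as far as the dominant eye is the right eye. If coded per subject, it should absorb essentially none of the shift. Section 14.5 does not say which coding is meant.

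Precision is at stake. The primary test is also the gate to both secondary tests (Section 14.4), so precision lost there bears on all three claims.

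**Working it through.** **Inputs from the documents.** 60 completers; primary difference −0.05 logMAR at two-sided 0.05; secondary difference 0.06 at two-sided 0.025; SDs and correlations from Table 9.

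**Assumed.** An OD–OS shift d of 0.01 to 0.08 logMAR (0.05 for AULCSF), since the documents give none. Exact 30/30 allocation.

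**1. Reproducing Table 9.** SD of the paired difference = sqrt(s1² + s2² − 2·r·s1·s2).
- SDs 0.08/0.09, r = 0.3: sqrt(0.0064 + 0.0081 − 0.00432) = 0.1009; SE = 0.1009/sqrt(60) = 0.0130.
- SDs 0.10/0.11, r = 0.3: sqrt(0.0100 + 0.0121 − 0.0066) = 0.1245; SE = 0.0161.

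Exact paired-t power at n = 60 is 96.5% and 86.4%, as printed. The rest of Table 9 also reproduces to 0.1 point.

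**2. Effect of leaving the term out.** Each difference is the lens effect plus or minus d, plus error. With an eye term, the residual SD is the value above on 58 degrees of freedom. Without it, the residual also carries d, and

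SE ratio (without/with) = sqrt(1 + (60/59)·d²/SD²).

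For d = 0.05 and SD 0.1245: sqrt(1 + 1.017 × 0.0025/0.0155) = 1.08. For SD 0.1009: sqrt(1 + 1.017 × 0.0025/0.01018) = 1.12.

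Power without the term was simulated with a noncentral chi-square residual sum of squares. Results at r = 0.3, with Table 9 SDs taken as free of the shift:

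| SDs (Test/Control) | Shift | SE too large by | Power without | Power with |
|---|---|---|---|---|
| 0.10/0.11 | 0.02 | 1.3% | 85.9% | 86.4% |
| 0.10/0.11 | 0.05 | 8% | 82.7% | 86.4% |
| 0.10/0.11 | 0.08 | 19% | 76.4% | 86.4% |
| 0.08/0.09 | 0.02 | 2.0% | 96.2% | 96.5% |
| 0.08/0.09 | 0.05 | 12% | 94.3% | 96.5% |
| 0.08/0.09 | 0.08 | 28% | 89.5% | 96.5% |

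At a shift of 0.01 the SE is only 0.3–0.5% too large. At r = 0.5 and a 0.05 shift, power is 92.5% against 95.1% (SDs 0.10/0.11) and about 98.5% against 99.4% (SDs 0.08/0.09).

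**3. Secondary endpoints** (r = 0.3, 0.05 AULCSF shift). Photopic, SD 0.11: about 86% against 89.5%. Mesopic, SD 0.15: about 59% against 62.6%.

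**4. Direction of the error.** Without the term, two-sided type I error at a 0.05 shift is 3.5% (SDs 0.10/0.11) or 2.9% (SDs 0.08/0.09), so the test is conservative. Imbalance adds little bias: at 33/27 the estimate moves by (33 − 27)/60 × 0.05 = 0.005 logMAR, which is 0.005/0.0161 = 0.3 to 0.005/0.0130 = 0.4 of an SE.

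**5. With dominance in the model** (coded per eye, 0.05 shift, r = 0.3). Regressing the difference on the dominance sign, with and without the eye sign, and assuming 65% right-dominant, gives power 82.3% against 86.0% (SDs 0.10/0.11) and 94.1% against 96.3% (SDs 0.08/0.09). The SE ratios are 1.07 and 1.11; at 80% right-dominant they are 1.05 and 1.07. A smaller simulation of the full planned mixed model, including the interaction and age (SDs 0.08/0.09, 120 runs per setting), gave 1.12, 1.11 and 1.07 at 50%, 65% and 80%.

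**6. Cost if there is no shift.** The term moves power from 86.43% to 86.41%.

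**The case against.** The strongest reply is that nothing here is an error. Randomising lens to eye in small blocks already protects the estimate, the test errs on the safe side, and adjusting for a balanced nuisance factor is an efficiency choice. That is right on validity, and this point claims no more.

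The shift is also hypothetical. No section reports one, and several features would limit it. Both eyes complete a full run without glare before any glare testing, so early practice falls largely outside the endpoints. Rests and patching are specified, strabismus and amblyopia are excluded, each eye must correct to 20/25 or better, and lens power is adjusted on over-refraction. Section 4.2 also points to a timing table (Table 1), whose contents could not be read in the text available. A 0.05 logMAR shift equals the whole lens difference that Section 14.5 calls clinically meaningful, and 0.08 is 1.6 times that. All of this stands: the loss may be trivial, and the 0.08 rows are an outer bound.

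Finally, Table 9 gives SDs by lens. With each lens on the right eye in about half of subjects, such SDs may already contain any OD–OS shift. On that reading (SDs 0.10/0.11, r = 0.3, residual SD = sqrt(0.0155 − d²)), power without the term is about 87%, 88% and 92% at shifts of 0.02, 0.05 and 0.08, so the planned 86.4% is met. This also stands: a shortfall against planned power is not established. Adding the term would still help, giving about 87%, 92% and 98%.

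**Conclusion.** The point holds as a recommendation on precision. Lens is randomised to eye, eye is identical to test order, and none of the three Phase 2 models adjusts for it. The lens estimate is unbiased under balanced allocation and no false superiority claim follows.

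The size depends on a shift that the documents do not give. It is negligible up to about 0.02 logMAR. At 0.05 and r = 0.3, with SDs free of the shift, the SE is 8–12% too large, and power falls by about 2 to 4 points on the primary and about 3 points in the secondary scenarios shown. Dominance coded per eye reduces the inflation somewhat but does not remove it. The case for acting is that the payoff is one-sided: next to nothing is lost if no shift exists, and precision is gained if one does.

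**What to change.** In Sections 14.5 and 14.6, add eye (OD/OS, equivalent to test order) as a fixed effect in the primary model and in both secondary AULCSF models. Keep lens type, dominant eye, their interaction and age. State whether dominant eye is coded per eye or per subject.

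The cost is one model term and about one degree of freedom in each model. Eye is already recorded and is the unit to which lens is randomised, so no new data, visits or procedures are needed. The change should be written in before unmasking, because Section 14.10 would treat a later addition as a change to be documented and justified in the study report.

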### Inclusion Criteria following Baseline Evaluation

6. The spherical equivalent of the subject's vertex-corrected distance refraction must be between -1.00 D and -6.00 D (inclusive) in each eye.
7. The magnitude of the cylindrical component of the subject's vertex-corrected distance refraction must be between 0.00 D and 1.00 D (inclusive) in each eye.
8. The best corrected, monocular, distance visual acuity must be 20/25 or better in each eye.

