**Clinical Study Protocol**  
**Johnson & Johnson Vision Care, Inc.**

Phase 2: Visit 1: Treatment 1 Lens Fitting		
Step	Procedure	Details
1.23	Lens Selection	
Assign the study lens based on the randomization scheme provided by the biostatistician.
 
Select the contact lens power [REDACTED] based on vertexed spherical equivalent from the refraction.

1.24	Lens Insertion	
The Investigator or the subject inserts the study lenses. Record the time of lens insertion.
 
Check for lens damage under the slit lamp before proceeding with lens settling.
 
Replace damaged lenses if applicable.
 
Ensure the subject is given a Patient Instruction Guide.

1.25	Lens Settling	Allow the study lenses to settle for a minimum of 5 minutes.
1.26	Subjective Best Sphere Over Refraction	Perform subjective best sphere refraction over the study lenses (adopt the maximum plus to maximum visual acuity (MPMVA) approach).
1.27	Lens Power Modification (if applicable)	
Adjust the lens power if the subject's best sphere over-refraction is not plano.
 
For each power modification, select the adjusted fitting lens power as appropriate and repeat steps 1.12 through 1.14.
 
Up to two power modifications are allowed per eye.

1.28	Subject Reported Ocular Symptoms	Subjects will respond to a verbal open-ended symptoms questionnaire.
1.29	Visual Acuity	Record the best corrected Snellen distance visual acuity to the nearest letter (OD and OS). Subjects must read the smallest line until at least 50% of the letters are read incorrectly. Visual acuity with the study contact lenses must be 20/30 or better OD and OS.

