**Clinical Study Protocol**  
**Johnson & Johnson Vision Care, Inc.**

1.33	
Visual Performance Testing Without Glare
	
Visual performance testing will be performed using the Metropsis system OD and OS in the following order. The eye not being tested will be patched.
 
Without glare OD:
 
 
1. Photopic resolution acuity           
 
A. Test distance: 4.0 m
 
B. Screen luminance approximately 120 cd/m^2
 
C. Ambient luminance must be dark with no lights or reflective surfaces within the general field of view of the target. EDC to record: Arcminute +/- SD. Range 0.2 - 60.0 arc minutes.
 
D. Rest a minimum of 2 minutes before next test
 
 
 
2. Photopic contrast sensitivity           
 
A. Test distance: 1.5 m
 
B. Screen luminance approximately 120 cd/m^2
 
C. Ambient luminance must be dark with no lights or reflective surfaces within the general field of view of the target
 
D. Spatial frequencies 3, 6, 9, 12, 18 using a 2 degree Gabor stimulus. EDC to record: contrast threshold mean +/- SD for each spatial frequency. Range 0.0000 – 100.0000.
 
E. Rest a minimum of 5 minutes before next test
 
 
 
3. Mesopic contrast sensitivity           
 
A. Test distance: 1.5 m
 
B. Screen luminance approximately 3 cd/m^2. This will be achieved by placing neutral density films over the Metropsis monitor.
 
C. Ambient luminance must be dark with no lights or reflective surfaces within the general field of view of the target
 
D. Spatial frequencies 1.5, 3, 6, 9, 12 using a 2 degree Gabor stimulus. EDC to record: contrast threshold mean +/- SD for each spatial frequency. Range 0.0000 – 100.0000.
 
 
 
	
------	---	---	--

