#### Hypothesis Testing

The null and alternative hypotheses for testing superiority of the Test lens relative to the Control lens with respect to photopic resolution acuity with a glare source are as follows:

$$H_0: \mu_T - \mu_C \geq 0$$
$$H_A: \mu_T - \mu_C < 0$$

Where,  $\mu_T$  represents the mean photopic resolution acuity (logMAR) for the Test lens and  $\mu_C$  represents the mean photopic resolution acuity (logMAR) for the Control lens. Statistical superiority will be declared if the upper bound of the adjusted 2-sided 95% confidence interval of the mean difference (Test – Control) is less than 0. A model-based point estimate of mean difference being -0.05 logMAR or more ( $\leq -0.05$  logMAR) will be considered clinically meaningful.

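### Cheap improvement, not an error: the Phase 2 primary model could use each eye's pre-assignment acuity to sharpen the lens comparison, which age cannot do when both eyes are observed.

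*Combined protocol and SAP*

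**What the plan says.** Section 14.5 analyses photopic resolution acuity with glare, in logMAR, in a linear mixed model with an unstructured covariance between a subject's two eyes. The terms are lens type, dominant eye and their interaction, plus age: "interaction of lens type by dominant eye will be included in the model as fixed effects and age as a covariate". No acuity measured before lens wear appears.

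Section 7.2 orders the Phase 2 visit as follows:

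- Step 1.19, baseline: "Complete subjective sphero-cylindrical refraction and record the resultant distance visual acuity (OD, OS, and OU) to the nearest letter".
- Step 1.20: eye dominance is determined.
- Step 1.23: "Assign the study lens based on the randomization scheme provided by the biostatistician".
- Step 1.29, on the study lenses: "Visual acuity with the study contact lenses must be 20/30 or better OD and OS".
- Step 1.33, also on the study lenses, without glare: "Visual performance testing will be performed using the Metropsis system OD and OS in the following order".

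Section 5.1 requires baseline information before randomization, allocates the two lenses to the two eyes of each subject, and stratifies by two age groups. Section 3.2.2 limits the baseline measure: "The best corrected, monocular, distance visual acuity must be 20/25 or better in each eye".

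**The concern.** In a contralateral design the lens effect is an interocular difference. A covariate can remove noise from that difference only if it differs between the two eyes. Age does not. Step 1.19 acuity does. It also precedes assignment, and it should be available for both eyes of every eligible subject because eligibility depends on it.

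What is at stake is precision only. The primary test gates both secondary hypotheses (Section 14.4). Section 14.2 says that no historical data exist for these endpoints with these lenses under this light source, so the SDs in Table 9 are borrowed from other instruments and conditions. If the true SD is nearer the upper planning value, some extra precision would be welcome.

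**Working it through.** **Inputs.** From Section 14.2 and Table 9: difference 0.05 logMAR, two-sided alpha 0.05, 60 completers, SDs (Test/Control) of 0.08/0.09 or 0.10/0.11, between-eye correlation ρ of 0.3 or 0.5. Section 14.5 uses the same 0.05 as its clinical margin: "A model-based point estimate of mean difference being -0.05 logMAR or more". One input is assumed: r, the correlation between the interocular difference in step 1.19 acuity and that in the endpoint. It is shown over 0 to 0.5.

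**1. Reproduce Table 9.** SD of the difference = √(s₁² + s₂² − 2ρs₁s₂). Weakest row: √(0.0100 + 0.0121 − 0.0066) = √0.0155 = 0.1245. The noncentrality is 0.05 / (0.1245/√60) = 3.11, and power from the noncentral t with 59 df is 86.4%, as printed. The other three rows at n = 60 also match: 95.1, 96.5 and 99.4%.

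**2. Age.** Both eyes have the same age, so age cancels from Test − Control. In simulated complete pairs (n = 60, SD 0.10/0.11, ρ = 0.3), the variance of the lens contrast with age, relative to without it, was 1.000.

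**3. Eye-level baseline.** Adjustment multiplies the variance of the contrast by (1 − r²) × 58/57. The factor 58/57, which is (n − 2)/(n − 3), allows for chance imbalance in the covariate. One further df is lost, leaving 58. Example, weakest row at r = 0.3: 0.1245 × √(0.91 × 58/57) = 0.1198, which gives 88.9%.

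| Table 9 row (SDs, ρ) | Planned | r = 0 | 0.1 | 0.2 | 0.3 | 0.5 |
|---|---|---|---|---|---|---|
| 0.10/0.11, 0.3 | 86.4% | 85.8 | 86.2 | 87.2 | 88.9 | 93.8 |
| 0.10/0.11, 0.5 | 95.1% | 94.8 | 95.0 | 95.5 | 96.4 | 98.5 |
| 0.08/0.09, 0.3 | 96.5% | 96.3 | 96.4 | 96.8 | 97.5 | 99.1 |
| 0.08/0.09, 0.5 | 99.4% | 99.3 | 99.3 | 99.5 | 99.6 | 99.9 |
| Variance factor | 1 | 1.018 | 1.007 | 0.977 | 0.926 | 0.763 |
| Effective completers | 60 | 59.0 | 59.6 | 61.4 | 64.8 | 78.6 |

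Effective completers = 60 / variance factor. Variances are equal at r = √(1 − 57/58) = 0.13.

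**4. Form of the covariate.** The planned model has one row per eye. In simulations of that model (60 complete pairs, weakest row, dominant-eye terms included), the variance of the lens contrast relative to no baseline term was:

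- interocular difference entered as a subject-level covariate: 1.000 at r = 0.3 and at r = 0.5;
- eye's own value plus the two-eye mean: about 0.92 at r = 0.3, and 0.74 to 0.78 across runs at r = 0.5, in line with the formula.

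The interocular difference is a single number per subject, so entered this way it cancels exactly as age does.

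**The case against.** The strongest reply is that the gain is speculative. Nothing in the documents supports r of 0.3 or more, and several features point to a low value:

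- Step 1.19 acuity follows sphero-cylindrical refraction, whereas the study lenses correct sphere only, in eyes with up to 1.00 D of cylinder (Section 3.2.2). Interocular differences from uncorrected cylinder reach the endpoint but not the covariate.
- The 20/25 floor and the exclusion of amblyopia and strabismus narrow the covariate's range.
- The endpoint is a Landolt C task under glare; the covariate is clinical acuity without glare.

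This stands. At r = 0.2 the gain is 0.8 points in the weakest row and 0.1 to 0.4 in the others.

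The treatment of age also has an answer. Age defines the randomization strata, which is an ordinary reason to include it. The cancellation is exact only with complete pairs: the ITT set needs just one observation (Section 14.3) and missing values are not imputed (Section 14.9), so age could matter slightly if an eye is missing. Nor is the model without eye-level information, because dominant eye varies within the pair and is determined before assignment. These points stand too, and they are why age should be kept. They do not alter the fact that a pre-assignment acuity for each eye is collected and left out.

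**Conclusion.** The point holds as an efficiency recommendation. With complete pairs, age does not change the precision of the lens contrast; step 1.19 acuity can. In the weakest row the change in power runs from −0.6 points at r = 0 to +2.5 at r = 0.3 and +7.4 at r = 0.5. The other rows start at 95% or more and gain at most 3.4 points. All of this rests on an assumed r, complete pairs and the Table 9 SDs.

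A reader might infer that the planned model is biased, that the stated power is wrong, or that age is a mistake. The documents support none of these: the lens is randomized to eye, all four primary powers at 60 completers reproduce, and age is a stratification factor. A reader might also see the absence of a planned lens comparison on the no-glare results as a gap. The Phase 2 objective, endpoints and hypotheses all concern performance with glare, so nothing formal is left untested.

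**What to change.** Before unmasking, add to the per-eye primary model the eye's own step 1.19 acuity, converted to logMAR, together with the subject's two-eye mean; or, equivalently for the lens contrast, the eye's signed deviation from that mean. Separating the two keeps one slope from mixing between-subject and between-eye relations. State the Snellen-to-logMAR rule, including how letters within a line are counted. Keep age.

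Do not enter the interocular difference as a subject-level covariate. Do not use acuity from step 1.29 or step 1.33, because both are measured on the assigned lenses and could absorb part of the lens effect.

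The cost is SAP wording on data already collected, the conversion, one degree of freedom for the within-pair contrast, and up to about 2% more variance (0.6 power points in the weakest row) if r is near 0.
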